7. ACTIONS REQUIRED FOR REPEAT EPISODES OF POTENTIAL HY'S LAW

This section is applicable when a patient meets PHL criteria on study treatment and has already met PHL criteria at a previous on study treatment visit.

The requirement to conduct follow-up, review and assessment of a repeat occurrence(s) of PHL is based on the nature of the alternative cause identified for the previous occurrence.

The investigator should determine the cause for the previous occurrence of PHL criteria being met and answer the following question:

• Was the alternative cause for the previous occurrence of PHL criteria being met found to be the disease under study e.g. chronic or progressing malignant disease, severe infection or liver disease, or did the patient meet PHL criteria prior to starting study treatment and at their first on study treatment visit as described in Section 6?

If No: Follow the process described in Section 4.2 of this Appendix

If Yes: Determine if there has been a significant change in the patient's condition[#] compared with when PHL criteria were previously met

- If there is no significant change no action is required
- If there is a significant change follow the process described in Section 4.2 of this Appendix

[#] A 'significant' change in the patient's condition refers to a clinically relevant change in any of the individual liver biochemistry parameters (ALT, AST or total bilirubin) in isolation or in combination, or a clinically relevant change in associated symptoms. The determination of whether there has been a significant change will be at the discretion of the Investigator, this may be in consultation with the Study Physician if there is any uncertainty.

Confidential Page 10 of 11

# **MODIFICATION HISTORY**

Unique	Date of the Document Version	Author	Significant Changes from
Identifier			Previous Authorized Version
for this			
Version			
1.0	02AUG2019	[name]	Not Applicable – First version
		[name]	
2.0	09FEB2024	[name]	Study Objectives: Added exploratory
		[name],	objectives
		[name],	Planned Analyses: Added discussion of dry
		[name]	run
		[name],	Analysis Sets:
		[name]	
 
Added clarification that EAS varies
 

		[name]	by both measure of interest and
			timepoint
			
 
Clairfied that EAS will be used in
 

			primary and effectiveness analyses
			General Considerations:
			
 
Updated software versions
 

			
 
Added discussion of when partial
 

			date imputations are applicable
			Output Presentations: Added discussion of
			additional data visualizations to be generated
			as needed and/or appropriate
			Dispositions and Withdrawals:
			Added analyses for patients
			receiving at least one dose of
			Metreleptin, patients valid for the

Document: Statistical Analysis Plan: AEGR-734-401: A 36-Month, Multicenter, Open Label Phase 4 Study to Evaluate the

Immunogenicity of Daily SC Metreleptin Treatment in Patients with Generalized Lipodystrophy

Author: [name], [name], [name], [name] Version Number: 2.1

EAS, and total study participation in
years
Demographic and Other Baseline
Characteristics: Added derivation for age at
informed consent
Medical History:

 
Updated definition of medical
 

history to align with the CRF.

 
Added derivation for age at
 

lipodystrophy diagnosis
Study Medicaiton Exposure: Updated
derivation for duration of exposure
accounting for interruptions
Primary Immunogenicity Analysis:

 
Added analysis set for the primary
 

analysis

 
Added descriptions of the primary
 

analyses to be performed

 
Added all relevant derivations for
 

primary analyses
Exploratory Analyses: Added fasting plasma
glucose and leptin/metreleptin concentration
as exploratory variables
Safety Outcomes:

 
Added definitions of AESIs
 

 
Added logic for selection of events
 

to include in AE tables stratified by
immunogenicity variables
Updated data windowing conventions
Updated partial date conventions

Document: Statistical Analysis Plan: AEGR-734-401: A 36-Month, Multicenter, Open Label Phase 4 Study to Evaluate the

Immunogenicity of Daily SC Metreleptin Treatment in Patients with Generalized Lipodystrophy

Author: [name], [name], [name], [name] Version Number: 2.1

Page 6 of 25

#### Statistical Analysis Plan

			•	Overall improvement of document structure, language and consistency
2.1	13MAR2024	[name]	•	Windowing conventions updated. There was
		[name],		an issue with some of the scheduled days.
		[name]		Now all of them are calculated as follows:
		[name]		floor (Study Month Number * 30.4).

Document: Statistical Analysis Plan: AEGR-734-401: A 36-Month, Multicenter, Open Label Phase 4 Study to Evaluate the

Immunogenicity of Daily SC Metreleptin Treatment in Patients with Generalized Lipodystrophy

Author: [name], [name], [name], [name] Version Number: 2.1

### 1. ABBREVIATIONS

ADA	Anti-drug antibody
AE	Adverse event
AESI	Adverse events of special interest
ATC	Anatomic therapeutic class
BMI	Body mass index
CI	Confidence interval
CRF	Case report form
DILI	Drug induced liver injury
EAS	Effectiveness analysis set
ECLIA	Electrochemiluminescence immunoassay
FAS	Full analysis set
HbA1c	Hemoglobin A1c
HuL	Human leptin
MEASuRE	Metreletpin Effectiveness and Safety Registry
MedDRA	Medical Dictionary for Regulatory Activities
MRD	Minimum required dilution
NAb	Neutralizing antibodies
PT	Preferred term
RB	Receptor blocking
RWES	Real-world evidence solutions
SAE	Serious adverse event
SAF	Safety analysis set
SAP	Statistical analysis plan
SC	Subcutaneous
SOC	System organ class
TEAE	Treatment emergent adverse event
TLFs	Tables, listings and figures
WHO-DD	World Health Organization Drug Dictionary

Document: Statistical Analysis Plan: AEGR-734-401: A 36-Month, Multicenter, Open Label Phase 4 Study to Evaluate the

Immunogenicity of Daily SC Metreleptin Treatment in Patients with Generalized Lipodystrophy

Author: [name], [name], [name], [name] Version Number: 2.1

Page 10 of 25

Statistical Analysis Plan

#### 2. INTRODUCTION

This statistical analysis plan (SAP) describes the rules and conventions to be used in the presentation and analysis of the effectiveness and safety data for Protocol AEGR-734-401: A 36-Month, Multicenter, Open Label Phase 4 Study to Evaluate the Immunogenicity of Daily Subcutaneous (SC) Metreleptin Treatment in Patients with Generalized Lipodystrophy. It describes the data to be summarized and analyzed, including specifics of the statistical analyses to be performed.

This SAP is based on the protocol number AEGR-734-401 V4.0, dated 08FEB2018 and case report forms (CRFs) V7.0, dated 28MAY2021. If there are differences between the statistical methods documented in the protocol and this document, the methods in this document will supersede what is in the protocol. Any changes from the planned analyses of the final SAP will be documented in the case study report.

#### 3. STUDY OBJECTIVES

### 3.1 Primary Objectives

The primary objective is to evaluate the immunogenicity associated with daily SC metreleptin treatment in patients with congenital or acquired generalized lipodystrophy.

### 3.2 Secondary Objectives

The secondary objective is to assess 2 methods of measuring in vitro neutralizing activity to metreleptin.

#### 3.3 Safety Objectives

The safety objectives are:

- To evaluate the safety and tolerability in relation to the development of or absence of antimetreleptin or anti-human leptin (HuL) antibodies, and/or *in vitro* neutralizing activity to metreleptin in patients with congenital or acquired generalized lipodystrophy.
- To measure *in vitro* neutralizing activity in all patients with suspected loss of response (worsening of metabolic control) or endogenous leptin action (severe infections or sepsis) at time of adverse event report.

Document: Statistical Analysis Plan: AEGR-734-401: A 36-Month, Multicenter, Open Label Phase 4 Study to Evaluate the

Immunogenicity of Daily SC Metreleptin Treatment in Patients with Generalized Lipodystrophy

Author: [name], [name], [name], [name] Version Number: 2.1

Page 11 of 25

Statistical Analysis Plan

## 3.4 Exploratory Objective

The exploratory objective is to evaluate the efficacy achieved with daily SC metreleptin treatment in patients with congenital or acquired generalized lipodystrophy.

#### 4. STUDY DESIGN

### 4.1 General Description

This study is an open-label, Phase 4 trial to provide an assessment of the immunogenicity associated with metreleptin and of any major potential risks due to development of antibodies to metreleptin. The study is being conducted to comply with an Food and Drug Administration post-marketing requirement.

Patients who have been prescribed metreleptin for generalized lipodystrophy, who meet all enrollment criteria and who have signed informed consent for this study at Screening (Visit 1) will receive the first dose of metreleptin at Enrollment/Baseline (Visit 2) at the study site. Patients will return to the study site for follow-up and collection of blood samples at regular intervals (at Month 1, 2, 4, 6, 9, 12, 18, 24, 30, and 36), for a total of 12 visits over approximately 3 years (36 months). Eleven patients who have been prescribed metreleptin will be enrolled.

All patients, including those with suspected loss of metreleptin efficacy (worsening of metabolic control) or endogenous leptin action (serious or severe infections or sepsis) should be tested for *in vitro* neutralizing activity.

The study flow diagram is presented in **Figure 1**.

Patients who sign informed consent and meet all inclusion/exclusion criteria will be enrolled in the study. Assessments will be made at the times specified in the Study Plan (**Table 1** of protocol). At the end of the 3-year study period, patients who still have *in vitro* neutralizing activity should enroll in the separate Immunogenicity Follow-up Program for continued immunogenicity monitoring.

[figure not shown]
Document: Statistical Analysis Plan: AEGR-734-401: A 36-Month, Multicenter, Open Label Phase 4 Study to Evaluate the

Immunogenicity of Daily SC Metreleptin Treatment in Patients with Generalized Lipodystrophy

Author: [name], [name], [name], [name] Version Number: 2.1

**Figure 1: Study Schematic** 

#### 4.2 Schedule of Events

The schedule of events can be found in **Table 1** of the protocol.

### 4.3 Changes to Analysis from Protocol

There are no changes to the analysis from the protocol.

### 5. PLANNED ANALYSES

The following analyses are planned for this study: 1) Final Analysis to be completed after database lock with 2) a dry run to be completed prior to database lock. The purpose of the dry run is to generate all analyses prior to database lock to ensure the planned analyses as described are appropriate. The dry run will use real study data. The results will not be shared with study sites. Any changes to the planned analyses based on the dry run will be documented in this SAP for

Document: Statistical Analysis Plan: AEGR-734-401: A 36-Month, Multicenter, Open Label Phase 4 Study to Evaluate the Immunogenicity of Daily SC Metreleptin Treatment in Patients with Generalized Lipodystrophy

Author: [name], [name], [name], [name] Version Number: 2.1

transparency. Given the key study endpoints are objective measures, the risk of bias as a result of the dry run is minimal.

#### 5.1 **Final Analysis**

All final, planned analyses identified in this SAP will be performed by IOVIA Real-World Evidence Solutions (RWES) Biostatistics following Sponsor Authorization of this SAP, Database Lock, and Sponsor Authorization of Analysis Sets.

#### 6. ANALYSIS SETS

#### 6.1 **Full Analysis Set (FAS)**

The full analysis set (FAS) will contain all enrolled subjects.

#### 6.2 Safety Analysis Set (SAF)

The safety analysis set (SAF) will contain all enrolled subjects who receive at least one documented dose of metreleptin and will be used in the assessment of safety.

#### 6.3 **Effectiveness Analysis Set (EAS)**

The effectiveness analysis set (EAS) will contain all enrolled subjects who received at least one documented dose of metreleptin and who have baseline and post-dose laboratory results on the measure of interest at the time point of interest. By definition, the EAS will vary by both measure and timepoint. The effectiveness analysis sets will be used in the primary and exploratory analyses.

#### 7. **GENERAL CONSIDERATIONS**

#### 7.1 **Baseline**

The Enrollment/Baseline Visit (Visit 2) is the baseline visit, and will be conducted within 28 days of the Screening Visit. First dose of metreleptin will be administered at Baseline after all procedures for the Screening Visit, specified in **Table 1** of the protocol, are conducted.

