6.2 Enrollment/Screening Period

6.2.1 Screening

At screening, consenting patients will be assessed to ensure that they meet eligibility criteria. Patients who do not meet these criteria must not be enrolled in the study.

- The Informed Consent and HIPAA Authorization forms, will be signed prior to performing any protocol-required procedures. The following will be conducted at the Screening Visit:
- Inclusion and exclusion criteria will be verified.
- Body weight and height will be measured as part of a complete physical exam.
- The patient's complete medical/surgical history will be recorded.
- All prior medications (prescription medications within 3 months) and current medications will be reviewed; concomitant use of lipid-lowering and antidiabetic will be recorded in the eCRF.
- Vital signs (sitting systolic and diastolic blood pressure and heart rate) will be measured.
- Urine will be collected for urinalysis.
- A serum or urine pregnancy test (βhCG) will be conducted for all female patients of childbearing potential.
- Fasting blood samples will be collected for the following assessments:
 - Chemistry and hematology.
 - HbA1c, lipids, and fasting glucose.

When all the screening results are available, individuals will be notified by telephone of their eligibility status. Those who qualify will be eligible to return to the clinical study site within 28 days after the Screening Visit to complete eligibility requirements for enrollment.

Prior to the Enrollment Visit (Visit 2), the Investigator should obtain certification under the REMS for MYALEPT to enable prescribing of metreleptin. Once the prescription for metreleptin is filled, the physician should have the first drug shipment sent to the physician's office in preparation for the Enrollment Visit.

Confidential Page 29 of 58

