## 8.2 Missing data

Generally, missing data will not be imputed. As applicable, partial dates may be imputed for the purposes of categorizing medications as prior/concomitant and defining treatment emergent adverse events (TEAEs). Partial date handling is described in **Appendix 1**. Imputed dates will NOT be presented in listings. Where applicable, counts of missing observations will be reported.

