#### 18.2 Exploratory Analysis Description, Derivations, and Definitions

Exploratory variables will be summarized using descriptive statistics (see **Section 8.1** Statistical Summaries, Tests and Confidence Intervals) and results will be presented as described below below:

- by visit
- as absolute change from baseline and percent change from baseline at each visit

HbA1c, fasting plasma glucose, and triglycerides will also be summarized by clinically relevant categories at each visit:

- $\circ$  hbA1c (<8%, >=8%)
- o fasting plasma glucose (<70 mg/dL, >=70 mg/dL and <=100 mg/dL, <100 mg/dL)

Document:	Statistical Analysis Plan: AEGR-734-401: A 36-Month, Multicenter, C	Open Label Phase 4 Study to Ev	aluate the
	Immunogenicity of Daily SC Metreleptin Treatment in Patients with	Generalized Lipodystrophy	
Author:	[name], [name], [name], [name]	Version Number:	2.1
		Version Date:	131// 1202/

o triglycerides (<500 mg/dl, >=500 mg/dl).

See Section 8.1 Statistical Summaries, Tests and Confidence Intervals for a description of statistics to be reported.

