#### 20. APPENDIX 2. WINDOWING CONVENTIONS

The below windowing conventions will be used to categorize all study assessments, including assessments occurring during unscheduled visits, into time periods of interest. Days are counted from the date of baseline visit where Baseline is defined as Day 0.

Only one assessment of each type will be presented from each analysis window. If more than one assessment of the same type occurs within an analysis window, then the maximum severity result will be selected for presentation. If more than one assessment of each types occurs within the maximum severity category, the result closest to the end of the analysis window will be selected. If the concept does not apply, then the result closest to the end of the analysis window will be selected.

The result closest to the end of the analysis window is preferred since the end of the analysis window aligns with the end of the visit window in all cases while the beginning of the analysis window may precede the beginning of the visit window. Therefore, the result closest to the end of the analysis window is most likely to be within the visit window.

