### Changes documented in 16Dec2024 version (prior to DBL)

1. Update definition of EAS from:

[E]nrolled subjects who received at least one documented dose of metreleptin and who have baseline and post-dose laboratory results on the measure of interest at the time point of interest.

To:

Enrolled subjects who received at least one documented dose of metreleptin and who have at least one anti-metreleptin/anti-HuL binding antibody (Antidrug Antibody (ADA) binding) result.

2. Update the following analysis from:

AEs, serious AEs (SAEs), AEs of special interest (AESIs), TEAEs, AEs possibly caused by metreleptin, and AEs leading to metreleptin discontinuation will be summarized by ADA positivity and titer, cell-based NAb positivity and titer, and RB positivity, titer, and quintile of percent inhibition.

To:

TEAEs, serious TEAEs, TEAEs that are AEs of special interest (AESIs), TEAEs possibly caused by metreleptin, and TEAEs leading to metreleptin discontinuation will be summarized by ADA positivity and titer, cell-based NAb positivity and titer, and RB positivity, titer, and quintile of percent inhibition.

3. Update analysis windows such that data collected for a CRF-defined visit are windowed according to the CRF-defined visit. Previously analysis windows ended on the same day as CRF-defined visit windows and extended CRF-defined windows to cover the calendar space since the last CRF-defined visit. Analysis windows are updated to extend CRF-defined visit windows to cover calendar space on either side of the CRF-defined visit window. See updated windows in Table 1 below.

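### SAP 7.1 makes Visit 2 the only baseline and states no Screening fallback, so a missing Visit 2 HbA1c, fasting glucose or triglyceride value costs that patient every change from baseline for that measure

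*SAP*

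**What the plan says.** - **Baseline.** SAP 7.1: "The Enrollment/Baseline Visit (Visit 2) is the baseline visit". SAP Appendix 2: "Days are counted from the date of baseline visit where Baseline is defined as Day 0". Both the window table in that appendix and the updated table in the change note put results from before Day 0 in a Screening window of their own.
- **Missing data.** SAP 8.2: "Generally, missing data will not be imputed". The only stated exception is partial dates. SAP 8.1 and 8.2 ask for counts of missing data where applicable.
- **Screening samples.** Protocol 6.2.1: "Fasting blood samples will be collected for the following assessments". The list under it covers chemistry, hematology, HbA1c, lipids and fasting glucose. Visit 2 follows within 28 days, and the first metreleptin dose is given there after sampling (Protocol 6.2.2).
- **Where change from baseline is used.** SAP 18.2 reports HbA1c, fasting plasma glucose, triglycerides and leptin/metreleptin concentration by visit and "as absolute change from baseline and percent change from baseline at each visit". Protocol 10.5 plans a change in HbA1c and a percent change in fasting triglycerides.
- **Effectiveness analysis set (EAS).** SAP 6.3 admits subjects "who have baseline and post-dose laboratory results on the measure of interest at the time point of interest" and adds: "By definition, the EAS will vary by both measure and timepoint". The 16Dec2024 change, made before database lock, replaces this with subjects "who have at least one anti-metreleptin/anti-HuL binding antibody (Antidrug Antibody (ADA) binding) result".

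**The concern.** In a study of 10 or 11 patients, one lost baseline matters. If a Visit 2 tube is lost or unusable for one test, the plan has no baseline for that patient and test. Every later change for that test is then undefined, although an untreated fasting result is already in the database.

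The 16Dec2024 change to the EAS also makes the loss harder to see. Under SAP 6.3 as written, a patient without a baseline result left the set for that measure, so the by-visit values and the changes described the same patients. Under the revised set the patient stays in the by-visit values but still has no change. The mean change then need not equal the difference between the visit mean and the baseline mean.

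**Working it through.** The plan gives no figure to reproduce here, so the check traces the text and then sizes the consequence.

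**Step 1: which measures are affected.**

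| Measure | Change from baseline planned? | Sampled at Screening? | Would a fallback help? |
|---|---|---|---|
| HbA1c | Yes (SAP 18.2) | Yes | Yes |
| Fasting glucose | Yes (SAP 18.2) | Yes | Yes |
| Triglycerides | Yes (SAP 18.2) | Yes | Yes |
| Leptin/metreleptin concentration | Yes (SAP 18.2) | No (Protocol Table 1) | No |
| Antibodies | No | No (Protocol Table 1) | No |
| Hematology, chemistry | No (SAP 17.4, Protocol 10.5: by-visit summaries) | Yes | Nothing to recover |

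**Step 2: whether the updated windowing supplies a fallback.** The 16Dec2024 change assigns data to the visit named on the case report form. That keeps a result recorded under Visit 2 at Visit 2. It does not turn a result recorded under Screening into a baseline, and the updated table still has separate Screening and Baseline rows.

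**Step 3: cost of one missing Visit 2 value, for one measure.** Inputs: N = 11 (SAP 4.1) or N = 10 (Protocol 4.2), and ten post-baseline visits (Months 1, 2, 4, 6, 9, 12, 18, 24, 30 and 36).

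- Share of patients lost = 1/N: 1/11 = 9.1%; 1/10 = 10.0%.
- Increase in the standard error of the mean change at a fixed SD = √(N/(N−1)) − 1: √(11/10) − 1 = 4.9%; √(10/9) − 1 = 5.4%.
- Visits affected: all ten. Changes for the other measures lose nothing.

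**Step 4: how often this might happen.** The documents give no rate. Assume a probability q that a given test is missing at a visit, with q from 0.02 to 0.10, the same at both visits and independent between visits and patients. The chance that at least one patient lacks a baseline is 1 − (1 − q)^N with Visit 2 only, and 1 − (1 − q²)^N with a Screening fallback.

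| q (assumed) | N = 11, Visit 2 only | N = 11, with fallback | N = 10, Visit 2 only | N = 10, with fallback |
|---|---|---|---|---|
| 0.02 | 19.9% | 0.4% | 18.3% | 0.4% |
| 0.05 | 43.1% | 2.7% | 40.1% | 2.5% |
| 0.10 | 68.6% | 10.5% | 65.1% | 9.6% |

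For example, with q = 0.05 and N = 11: 1 − 0.95^11 = 43.1%, and 1 − (1 − 0.0025)^11 = 2.7%.

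**The case against.** The best defense is that a single Visit 2 baseline is a legitimate choice. Protocol 6.2.2 specifies an 8-hour overnight fast, a delayed morning antidiabetic dose and sampling before the first dose. The Screening section says only that samples are fasting. A fallback would mix baselines taken under somewhat different conditions and up to 28 days apart. Visit 2 is also a supervised site visit, no document reports a missing value there, and the missing counts would disclose any gap. All of this stands and limits the weight of the point. It does not remove the point, because disclosure does not recover the lost changes and a flagged fallback shows the reader which baselines differ.

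The silence on a fallback also cannot be confirmed in full. Parts of the change note and the table shells were not available, and further changes were added on 26Feb2025.

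A reader might draw four stronger conclusions that the documents do not support:

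- **All of the patient's change results are lost.** The loss is confined to the test with the missing value.
- **Safety laboratory results are affected.** SAP 17.4 summarizes them at each visit and plans no change from baseline.
- **The SAP forbids or discards Screening data.** It names a baseline visit and is silent on a substitute. Screening keeps its own window.
- **The case rests on the gain in precision from two pre-dose values.** Averaging them would reduce the error variance of a change from 2 to 1.5 units, or 25%, if errors were equal and independent. That is a different proposal and has no bearing on a missing value.

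**Conclusion.** The point holds as a low-cost improvement to exploratory, descriptive results. On the available text, a missing Visit 2 value for HbA1c, fasting glucose or triglycerides removes that patient from that measure's changes at every visit, although a usable pre-dose value exists. The cost per occurrence is one patient in 10 or 11 and a standard error about 5% larger. The standard-error figure assumes that the SD is unchanged by the loss. How often it happens is unknown, and the 18% to 69% range for Visit 2 only depends entirely on the assumed q. The primary immunogenicity analysis is unaffected. If every Visit 2 value is present, no result changes.

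**What to change.** First check whether any Visit 2 HbA1c, fasting glucose or triglyceride value is missing. Then amend SAP 7.1:

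- For these three measures, baseline is the last non-missing value before the first metreleptin dose: Visit 2, otherwise Screening.
- Flag each patient and measure for which a Screening value is used.
- For glucose, add a footnote that delaying the morning antidiabetic dose is specified at Visit 2 but not at Screening.
- Keep Visit 2 as the only baseline for leptin and antibodies, which have no Screening sample.

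The cost is a short addition to the SAP, a flag and a footnote. The downside is that a fallback value can be up to 28 days older and taken under slightly different conditions. The change note records database lock as already past by 26Feb2025, so a rule adopted after lock should be documented as a post-lock change.
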